### 12.1 Assessments

Data will be collected by members of the research team, except for the therapists rated fidelity checklist which will be completed by therapists themselves and returned to the study team.

A schematic diagram (Figure 3) illustrates the study timelines for participants for Phase 2 only.

# Figure 2. Schedule of enrolment, interventions and assessments

Procedures	Study timepoints								
	Screening	Baseline	Treatment Phase	Follow Up					
Informed consent	Х								
Demographics	Х								
Medical history	Х								
Eligibility assessment,									
including completion of									
Vineland Adaptive Behaviour	х								
Scales 3 and confirmation of	^								
a diagnosis of Specific									
Phobia (symptom checklist)									
Delivery of intervention			Х						
Fidelity			X (therapist completed)						
Phobia symptom checklist		x		Х					
Severity Measure for Specific Phobia		x		х					
Impact supplement (SDQ)		x		Х					
Specific Phobia Diagnosis		x		Х					
Emotional and Behavioural Problems		x		х					
Challenging Behaviour		x		Х					
Medication		x		Х					
Adverse event assessments (if required)			x	х					

<sup>1 Taken from the HRA CTIMP protocol template (2016).

Reading I F University of East Anglia

Coventry and

Semi-structured interviews		Х

## 12.2 Follow-up

There is only a single follow-up period for this study which is within 4-weeks of the completion of the intervention. For participants who discontinue treatment, and wish to remain enrolled in the study, data will be captured as per protocol. This means that data will be captured within the 4-week period following when treatment would have been completed had the participant continued to take part in the intervention.

Semi-Structured Interviews. We will examine the views of parents/carers and therapists to address key questions. Interviews will address: (a) intervention accessibility and acceptability, (b) helpful / unhelpful aspects, including barriers to change, (c) the value of our adaptations, (d) relationships with therapists within intervention, (e) acceptability of consent processes, (f) acceptability of outcome measures, and (g) acceptability of randomisation within a future trial. We will complete semi-structured interviews with up to 10 parents/carers and up to 10 therapists.

We will also complete interviews with up to 5 young people who received the intervention to explore their experience of the intervention and the outcomes for them. We recognise that interviewing participants with moderate-severe LD may be difficult due to associated communication difficulties and, for some participants with severe LD, they may not be able to take part within an interview process. We will make use of augmented communication methods to aid our interview as much as possible, such as Talking Mats which is a structured approach to helping people with communication difficulties to organise and express their views; these methods have been used previously with this population (60). For those who are not able to take part in Talking Mats-based interviews, we will rely on interviews with parents/carers.

## 13 Safety reporting

The Principal Investigator is responsible for ensuring that all site staff involved in this study are familiar with the content of this section. This section applies only to Phase 2 of the study.

All SAEs must be reported immediately (and within 24 hours of knowledge of the event) by the PI at the participating site to Study Team unless the SAE is specified as not requiring immediate reporting (see section 13.2).

NHS Co Warwickshire I

#### Definitions 13.1

WARWICK

Term	Definition
Adverse Event (AE)	Any untoward medical occurrence in a participant or study participant administered an intervention which are not necessarily caused by or related to that product
Serious Adverse Event (SAE)	
 
Any adverse event that -
 
Results in death
 
Is life-threatening*
 
Required hospitalisation or prolongation of existing hospitalisation**
 
Results in persistent or significant disability or incapacity
 
Consists of a congenital anomaly or birth defect
 
Other medically important condition***
 

Serious Adverse Reactions (SARs) Suspected Unexpected Serious Adverse Reactions (SUSARs)	

Any SAE occurring in a study participant for which there is a reasonable possibility that it is related to the intervention.

A SAR, the nature and severity of which is not consistent with the Reference Safety Information (RSI) for the intervention.

\*Note: The term 'life-threatening' in the definition of serious refers to an event in which the study participant was at risk of death at the time of the event or it is suspected that used or continued used of the product would result in the subject's death; it does not refer to an event which hypothetically might have caused death if it were more severe.

\*\* Note: Hospitalisation is defined as an inpatient admission, regardless of the length of stay, even if the hospitalisation is a precautionary measure for continued observation. Pre-planned hospitalisation e.g. for pre-existing conditions which have not worsened, or elective procedures, does not constitute an SAE.

\*\*\* Note: other events that may not result in death, are not life-threatening, or do not require hospitalisation, may be considered as an SAE when, based upon appropriate medical judgement, the event may jeopardise the participant and may require medical or surgical intervention to prevent one of the outcomes listed above.

Reading C Last Anglia

## 13.2 Causality

The Principal Investigator (or another delegated qualified member of the trial team) will assess each SAE to determine the causal relationship and the Chief Investigator (or another appropriately qualified member of the Study Management Group) can also provide this assessment where necessary:

Relationship	Description	Reasonable possibility that the SAE may have been caused by the intervention?
Unrelated	There is no evidence of any causal relationship with the intervention	No
Unlikely	There is little evidence to suggest there is a causal relationship with the intervention (e.g. the event did not occur within a reasonable time after administration of the trial medication). There is another reasonable explanation for the event (e.g. the participant's clinical condition, other concomitant treatment).	No
Possible	There is some evidence to suggest a causal relationship with the intervention (e.g. because the event occurs within a reasonable time after administration of the trial medication). However, the influence of other factors may have contributed to the event (e.g. the participant's clinical condition, other concomitant treatments).	Yes
Probable	There is evidence to suggest a causal relationship and the influence of other factors is unlikely.	Yes
Definite	There is clear evidence to suggest a causal relationship and other possible contributing factors can be ruled out.	Yes

NHS entry and

Cove vickshire Pa Reading E Vniversity of East Anglia

abilities Evelina London

The causality assessment given by the Principal Investigator (or delegate) cannot be downgraded by

the Chief Investigator (or delegate), and in the case of disagreement both opinions will be provided.

## 13.3 Expectedness

WARWICK

The Chief Investigator (or another delegated appropriately qualified individual) will assess each SAE to perform the assessment of expectedness.

SAEs which add significant information on specificity or severity of a known, already documented adverse event constitute unexpected events. For example, an event more specific or more severe than that described in the protocol is considered unexpected.

	Expected Events
Anxiety and/or distress	Participants are expected to experience some anxiety and/or distress associated with engagement in the treatment (graded exposure to fear stimulus). This could be of a nature and degree such that exposure must be discontinued to prevent further escalation of anxiety and/or distress. Should this happen, the graded hierarchy of fears governing exposure work would be expanded such that any associated anxiety and/or distress is reduced.
Challenging behaviour	There may be a temporary increase in challenging behaviour associated with some exposure work. This should not be of a nature or degree such that others or an individual is placed at serious risk of harm.

## **13.4** Reporting procedures

## 13.5.1 Participating Site Responsibilities

The PI (or delegated appropriately qualified member of the study team team) should sign and date the SAE Reporting Form (see Appendix) to acknowledge that they have performed the seriousness and causality assessments. Investigators should also report SAEs to their own Trust in accordance with local practice and this may involve the completion of an additional form.

Reading L Last Anglia

A completed SAE form for all events requiring immediate reporting should be submitted via email to [contact] within 24 hours of knowledge of the event. A separate form must be used to report each event, irrespective of whether the events had the same date of onset.

The participant will be identified only by participant number, partial date of birth (mm/yy) and initials. The participant's name should not be used on any correspondence.

It is also required that sites respond to and clarify any queries raised on any reported SAEs and report any additional information as and when it becomes available through to the resolution of the event. Additionally, the study team may request additional information relating to any SAEs and the site should provide as much information as is available to them in order to resolve these queries.

Serious Adverse Event (SAE) email address:

[contact]

Serious adverse events should be reported from time of signature of informed consent, throughout the treatment period up to, and including 40 days after the participant has stopped receiving the intervention.

An SAE form is not considered as complete unless the following details are provided:

- Full participant number
- An Adverse Event
- A completed assessment of the seriousness, and causality as performed by the PI (or another appropriately medically qualified doctor registered on the delegation log).

If any of these details are missing, the site will be contacted, and the information must be provided by the site to the study team within 24 hours.

All other AEs should be reported on the CRF following the CRF procedure described in Section 16.

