### 13.5.2 The study team responsibilities

Following the initial report, all SAEs should be followed up to resolution wherever possible, and further information may be requested by the study team. Follow up information must be provided on a new SAE form.

**Evelina**London

Reading East Anglia

The study team will continue reporting SAEs until 40 days after the participant receives the last part of the intervention.

Once an SAE is received by a member of the study team, evaluated, and sent to the Chief Investigator (or their delegate) for an assessment of expectedness.

Only reports of related and unexpected Serious Adverse Events (SAEs) will be submitted to the REC. These should be sent within 15 days of the Chief Investigator becoming aware of the event. There is no further requirement for annual safety reports in addition to the information provided through the annual progress report.

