# 18 End of Study definition

The treatment phase will be followed by a 4-week follow-up period. This will continue until the last participant completes the intervention and the final outcome assessment within this 4-week follow-up period.

The end of the study is defined as the date of final data capture to meet the study endpoints. In this case end of study is defined as the date that the last participant completes the intervention and the final outcome assessment within the 4-week follow-up period having also completed any associated semi structured interviews.

The sponsor must notify the main REC of the end of a study within 90 days of its completion or within 15 days if the study is terminated early.

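### The 40-day SAE reporting window is not aligned with the end-of-study definition, nor with follow-up timing for families who stop treatment early

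*Protocol*

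**What the plan says.** The Protocol sets four timings for Phase 2.

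- **SAE reporting, sites (section 13.5.1):** from consent "up to, and including 40 days after the participant has stopped receiving the intervention".
- **SAE reporting, study team (section 13.5.2):** "The study team will continue reporting SAEs until 40 days after the participant receives the last part of the intervention".
- **Follow-up (section 12.2, with the same window in section 10.2):** "There is only a single follow-up period for this study which is within 4-weeks of the completion of the intervention". Where a family stops treatment early but remains enrolled, data are captured "within the 4-week period following when treatment would have been completed had the participant continued".
- **End of study (section 18):** reached once "the last participant completes the intervention and the final outcome assessment within the 4-week follow-up period having also completed any associated semi structured interviews".

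In Figure 2, the schedule has a row "Adverse event assessments (if required", marked for the treatment phase and follow-up. The text does not explain the qualifier. No contact is scheduled at day 40, and the interviews are given no window of their own.

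**The concern.** The rules use two window lengths, 40 days and 4 weeks, and two starting points, actual stopping and planned completion. Nothing says how they fit together, and two problems follow.

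First, the study can be declared ended while sections 13.5.1 and 13.5.2 still require SAEs to be reported for the last participant or participants.

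Second, a family that stops early can still be enrolled and awaiting follow-up after its SAE window has closed. A serious event in that interval falls outside the stated reporting duty, even if it comes to light at the follow-up assessment. Section 13.3 expects that distress may be enough to require exposure to be discontinued. If a family left treatment for that reason, this rule would apply to it.

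The study is small (up to 20 children) and descriptive. What is at stake is whether its safety record covers a clearly defined period for every child.

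**Working it through.** The check is calendar arithmetic. The plan derives no figure here that could be reproduced; the 40 days and the 4 weeks are simply stated.

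**Inputs**

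- SAE window: 40 days after the last intervention received (sections 13.5.1 and 13.5.2).
- Follow-up window: 4 weeks = 28 days, from completion or, for early stoppers, from planned completion (section 12.2).
- Intervention length: a one-day workshop, then up to 8 weekly calls (section 11.2, description of the intervention). Taking the workshop as day 0, planned completion is about T = 8 × 7 = 56. The interval from workshop to first call is not stated, so T = 49 and T = 63 are shown as a range.

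**Completers**

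- Follow-up on the last permitted day: 40 − 28 = 12 days of SAE window remain.
- Follow-up on the day of completion: 40 − 0 = 40 days remain.

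Every completer therefore has 12 to 40 days of SAE window after follow-up with no scheduled safety contact. For the last participant, if a completer, the study can end 12 to 40 days before the window closes, unless an interview delays it.

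**Early stoppers who stay in data collection**

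Let s be the day of stopping, counted from the workshop.

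- The SAE window closes on day s + 40.
- Follow-up is permitted from day T to day T + 28.
- The window closes before any permitted follow-up if s + 40 < T, that is s < T − 40.
- It closes before the latest permitted follow-up if s + 40 < T + 28, that is s < T − 12.

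| Planned completion T | Follow-up days | Closes before any follow-up if s is below | Closes before latest follow-up if s is below | Gap if stopping right after the workshop (s = 0) |
|---|---|---|---|---|
| 49 | 49–77 | 9 | 37 | 9–37 days |
| 56 | 56–84 | 16 | 44 | 16–44 days |
| 63 | 63–91 | 23 | 51 | 23–51 days |

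For T = 56 and s = 0, the window closes on day 40. The gap is 56 − 40 = 16 days to the earliest follow-up and 84 − 40 = 44 days to the latest. Moving T by a week shifts the cut-offs but does not remove the gap.

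**The case against.** A 40-day window that outlasts a 28-day visit is not in itself a contradiction. Reporting is triggered by knowledge of the event, not by a visit, and treatment is delivered within NHS services whose clinicians may learn of events. A reader might infer that days 29 to 40 are unobserved. The documents do not support that: those days lack a scheduled safety contact, but events that become known must still be reported. Some families will also be interviewed, possibly in that period. This part of the objection stands.

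On closure, section 18 also waits for interviews that have no stated window, so the study may end later than day 28. Section 13.5.2 obliges the study team to continue to day 40, and nothing says that duty stops at closure. This limits the point to the last participant or participants, and to a possibility. It does not reconcile the two rules.

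On early stoppers, it is defensible to count safety reporting from the last exposure and outcomes from planned completion, since the two serve different purposes. The 16 to 44 days is a worst case: it needs a stop right after the workshop and a family that stays in data collection. Even so, the knowledge trigger is no answer here, because the reporting duty itself has lapsed.

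A reader might also infer that a harm rate would be under-counted. The Protocol lists no harm rate among its outcomes (section 5.2) and has no safety threshold in its progression criteria (section 14.7), so that goes too far. Nor does the qualifier in Figure 2 show that families are not asked about adverse events. It may only mean that a form is completed when an event occurs, so the text does not establish a need for an adverse event question at every call.

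**Conclusion.** The point holds as a conflict between stated timing rules, and it should be put right.

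- **Closure:** followed as written, the study can end at least 12 days before SAE reporting is due to close for the last participant or participants. This assumes that the last participant completes treatment and that interviews do not delay the end.
- **Early stoppers:** the reporting duty can lapse while the child is still enrolled and awaiting follow-up. The size of this gap rests on planned completion at about day 56 and applies only to families that stay in data collection.
- **Completers between follow-up and day 40:** this is an absence of scheduled safety contact, not of a reporting duty.

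The conclusion concerns what the rules permit. It does not show that any event would be missed.

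**What to change.** Reconcile sections 12.2, 13.5.1, 13.5.2 and 18 so that two conditions hold:

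1. SAE reporting does not lapse before a participant's follow-up assessment. One way is to run it to the later of day 40 after the last intervention and the follow-up assessment.
2. The study does not end before the last participant's SAE window has closed.

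In Figure 2, state what the qualifier on the adverse event row means: whether the question is always put, or a form is completed only when an event has occurred.

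The choice of window is for the sponsor. The changes are to reporting and closure wording and leave treatment untouched. Closure may move by 40 − 28 = 12 days, about 2 weeks, beyond the latest permitted follow-up. It may move by up to 40 days if the last follow-up is done on the day of completion.

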### 13.5.2 The study team responsibilities

Following the initial report, all SAEs should be followed up to resolution wherever possible, and further information may be requested by the study team. Follow up information must be provided on a new SAE form.

**Evelina**London

Reading East Anglia

The study team will continue reporting SAEs until 40 days after the participant receives the last part of the intervention.

Once an SAE is received by a member of the study team, evaluated, and sent to the Chief Investigator (or their delegate) for an assessment of expectedness.

Only reports of related and unexpected Serious Adverse Events (SAEs) will be submitted to the REC. These should be sent within 15 days of the Chief Investigator becoming aware of the event. There is no further requirement for annual safety reports in addition to the information provided through the annual progress report.

#### 13.7 **Urgent Safety Measures (USMs)**

An urgent safety measure is an action that the Sponsor, Chief Investigator or Principal Investigator may carry out in order to protect participants against any immediate hazard to their health or safety. Any urgent safety measure relating to this trial must be notified to the Research Ethics Committee immediately by telephone, and in any event within 3 days in writing, that such a measure has been taken.

# **14 Statistical considerations**

#### 14.3 Sample size

Phase 1a: We will establish an Intervention Adaptation Group (IAG) comprised of 6 to 8 key stakeholders who will be representatives from our PPI partners, carers and family members, people with LD, and clinicians, along with members of the research team. These participants will work with use to adapt and refine our intervention, measures, and fidelity checklist. There are no research data for formal analyses being collected from these participants.

Phase 1b: We will collect data about TAU from a minimum of 50 parents, together with LD health professionals, service providers, and commissioners).

Phase 2: We will recruit up to 20 participants and their parental caregivers in total. As this is a feasibility study, and the purpose is to provide estimates of key parameters for a future pilot trial rather than to power the current study to detect statistically significant differences, a formal a priori power calculation will not be conducted (54).

### 14.7 Progression criteria

The study will estimate key parameters for a future trial that will be used to inform HTA decisionmaking with regard to advertising for a future trial and will assist researchers in developing proposals for a future trial. We propose the following progression criteria with reference to several key indicators of success: (a) recruitment, (b) protocol adherence, and (c) outcome data. These have been incorporated into three possible recommendations regarding feasibility of a larger trial (63).

Evelina London

**Green.** If all of the following criteria are met, the Study Steering Committee (SSC) will consider a recommendation that a larger trial is feasible:

(a) Recruitment: (i) accrual rate is at least 3 patients per site per month on average, and (ii) attrition rate is 30% or lower,

(b) Protocol adherence: (i) fidelity ratings indicate therapist adherence to the intervention of at least 75%, (ii) at least 70% of parents/carers and clinicians report that the intervention and consent procedures were acceptable, and (iii) at least 90% of participants received the intervention, and

(c) Outcome data: (i) at least 75% of participants complete outcome measures at each time point, (ii) at least 75% of items across outcome measures for each participant are complete, and (iii) at least 75% of parents/carers judge the outcome measures to be acceptable.

**Amber.** If any of the following criteria are met, then the research team will examine the reasons for this, carefully consider what remedial action can be taken to improve the likelihood that a larger trial is feasible, and provide this analysis to the SSC for consideration. For example, difficulties may be related to a delay in research ethics or governance approvals or a longer than expected time to build relationships with referrers which could be managed effectively within a larger trial:

(a) Recruitment: (i) accrual rate is less than 3 but greater than 2 patients per site per month on average, or in the later recruitment months the accrual rate reaches 3/month and (ii) attrition rate is greater than 30% but less than 50%,

(b) Protocol adherence: (i) fidelity ratings indicate therapist adherence to the intervention is less than 75% but greater than 60%, (ii) less than 70% but greater than 55% of parents/carers and clinicians report that the intervention and consent procedures were acceptable, and (iii) less than 90% but greater than 70% of participants received the intervention

(c) Outcome data: (i) less than 75% but greater than 60% of parents/carers complete outcome measures at each time point, (ii) less than 75% but greater than 60% of items across outcome

measures for each participant are complete, and (iii) less than 75% but greater than 65% of parents/carers judge the outcome measures to be acceptable.

**Red.** If any of the following criteria are met, and following a thorough review of the reasons for this, including consideration as to whether remedial action could be taken, a recommendation to not proceed to a larger trial may be made by the SSC:

Reading A University of East Anglia

(a) Recruitment: (i) accrual rate is less than 2 patients per site per month on average, and (ii) attrition rate is greater than 40%,

(b) Protocol adherence: (i) fidelity ratings indicate therapist adherence to the intervention is less than 50%, (ii) less than 55% of parents/carers and clinicians report that the intervention and consent procedures were acceptable, and (iii) less than 60% of participants received the intervention, and

(c) Outcome data: (i) less than 50% of parents/carers complete outcome measures at each time point, (ii) less than 50% of items across outcome measures for each participant are complete, and (iii) less than 65% of parents/carers judge the outcome measures to be acceptable.

All recommendations will be made to the Study Steering Committee, including our analysis of associated barriers and proposed remedial action

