# 1 Amendment History

The following amendments and/or administrative changes have been made to this protocol since the implementation of the first approved version.

Version approved by the ethics committee was 3.0.

Amendment No.	Protocol version no.	Date issued	Summary of changes made since previous version
1	3.1	28.07.2021	- We have added an option to offer the telephone interviews with professionals as an online survey. The questions remain the same.

shire and Worce

Coventry and ershire Warwickshire Partnership

#### Synopsis 2

Short title	Treating specific phobias		
Acronym	SPIRIT		
Internal ref. no.	Ideate: 64325		
Development phase	Feasibility		
Funder and ref.	National Institute for Health Research - Ref: NIHR130177		
Study design	Phase 1a: intervention adaptation. Phase 1b: online survey and interviews to describe treatment as usual (TAU). Phase 2: single-arm feasibility study		
Study participants	
 
Phase 1a: Intervention Adaptation Group (IAG) will be comprised of 6-8 key stakeholders who will be representatives from our PPI partners, carers and family members, young people with learning disabilities, and clinicians, along with members of the research team.
 
Phase 1b: parents who identify their child with moderate–severe learning disability as having a specific phobia, learning disability professionals (health professionals, service providers, and commissioners)
 
Phase 2: Children and adolescents aged 5-15 years, with a diagnosis of moderate–severe learning disability who have a suspected specific phobia (confirmed at screening), together with their parental caregiver(s).
 
		
Planned sample size	Phase 1a: 6 to 8. Phase 1b: minimum of 50 parents, 25 learning disability professionals. Phase 2: 20 participants and their parental caregivers (20)		
Planned number of sites	Phase 1b: up to 20 sites for survey of TAU Phase2: 2 sites for recruitment of participants for intervention modelling		
Inclusion criteria	
 
Phase 1b: parents who identify their child with moderate–severe learning disability as having a specific phobia.
 
Phase 2: (a) diagnosis of moderate–severe LD confirmed at screening, (b) diagnosis (DSM-5) of specific phobia, confirmed at screening, (c) parent/carer able to participate in the intervention.
 
		

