#### 9.3 Recruitment rates and Retention

Our overall planned accrual rate is approximately 3 participants per month over seven months, to reach our aim of a final sample size of 20.

We will make use of multiple strategies to promote retention that have proved successful in our previous research studies, including: (a) maintaining regular contact with participants, and minimising the time between contacts, (b) promoting service-user involvement at all stages of the study, (c) using co-production to develop the intervention to help encourage retention, (d) working effectively with the charitable sector to help encourage continued engagement.

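### The accrual progression bands are set per site but the recruitment plan is set overall, so a study that recruits exactly to plan cannot be Green and falls below the Red accrual cut

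*Protocol*

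**What the plan says.** Recruitment plan. Section 9.3 of the protocol states: "Our overall planned accrual rate is approximately 3 participants per month over seven months", with a final sample of 20 as the aim. Section 14.3 states: "We will recruit up to 20 participants and their parental caregivers in total". The Synopsis (Section 2) lists, for Phase 2, "2 sites for recruitment of participants for intervention modelling".

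Progression criteria (Section 14.7), accrual item:

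- Green, for which every listed criterion must be met: "accrual rate is at least 3 patients per site per month on average".
- Amber, for which any one listed criterion is enough: "accrual rate is less than 3 but greater than 2 patients per site per month on average", with the alternative "or in the later recruitment months the accrual rate reaches 3/month". Both are then linked by *and* to attrition above 30% and below 50%.
- Red, also introduced by an any-one rule: "accrual rate is less than 2 patients per site per month on average, and (ii) attrition rate is greater than 40" per cent. A recommendation against a larger trial *may* follow, after a review of the reasons and of possible remedies.

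The three main bands are therefore in participants per site per month. The plan and the Amber alternative carry no per-site qualifier.

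**The concern.** The criterion should tell the Study Steering Committee and the funder whether recruitment went well enough to support a larger trial. A sensible threshold puts delivery of the plan in, or at the edge of, the top band. Here the plan and the threshold use different units, and with two sites the units differ by a factor of two. Recruitment that goes exactly as intended would be reported as failing Green and as below the rate that the protocol associates with not proceeding.

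Accrual is the first criterion listed, and Section 14.7 says that the criteria will inform the funder's decision on a future trial. If the thresholds are reinterpreted only after the accrual figures are in, the change will look driven by the result.

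**Working it through.** **Inputs.** Overall planned rate, about 3 per month for 7 months (Section 9.3). Target and cap, 20 (Sections 9.3 and 14.3). Sites, 2 (Synopsis). Per-site cuts, 3 for Green and 2 for Red (Section 14.7). Assumption not stated in the protocol: both sites recruit for all seven months, giving 2 × 7 = 14 site-months.

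**Step 1: reproduce the plan.** 3 × 7 = 21, against the stated 20. In reverse, 20 / 7 = 2.86 per month, which is approximately 3. Section 9.3 is consistent within itself.

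**Step 2: put the plan in the unit of Section 14.7.**

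- At 3 per month: 3 / 2 = 1.50 per site per month.
- At 20 in seven months: 20 / 14 = 1.43 per site per month.

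Both are below 3 (not Green), not above 2 (outside the per-site Amber band), and below 2 (under the Red accrual cut).

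**Step 3: what the bands demand with two sites.**

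| Requirement | Overall rate | In 7 months | Time to recruit 20 |
|---|---|---|---|
| Plan | 2.86 to 3 per month | 20 to 21 | 7 months |
| Reach the Red cut | 2 × 2 = 4 per month | 28 | 20 / 4 = 5 months |
| Reach Green | 3 × 2 = 6 per month | 42 | 20 / 6 = 3.3 months |

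Because 20 is a cap, 28 or 42 recruits cannot occur. The only way to reach either rate is to finish early.

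**Step 4: chance of each outcome if the plan is right.** Assume Poisson accrual at 3 per month overall, with recruitment stopping at 20.

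- Green accrual needs 20 recruits by 3.33 months, with 3 × 3.33 = 10 expected: P(Poisson(10) ≥ 20) = 0.0035, about 0.3%.
- Below the Red cut means 20 not reached by 5 months, with 3 × 5 = 15 expected: P(Poisson(15) ≤ 19) = 0.875, about 88%.

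The second figure is the chance of falling below the accrual cut. It is not the chance of a Red classification.

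**Step 5: how the accrual result feeds into the bands.**

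- *Each numbered item is a separate trigger.* On-plan accrual meets the Red accrual item. If the Amber alternative is read as an overall rate, on-plan accrual meets that item as well, because 3 per month is the planned rate.
- *Accrual and attrition are required jointly.* An on-plan study with attrition of 30% or lower is not Green on recruitment, not Amber (attrition too low) and not Red (attrition too low). It has no recruitment class. A study with almost no accrual but low attrition would also avoid Red.

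Green fails under both readings, because it requires every criterion.

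**Step 6: would changing the unit alone be enough?** If the same numbers are read as overall rates, a steady 3.0 per month just meets Green, but exactly 20 in seven months (2.86) falls in Amber. Under the Poisson assumption, reaching 20 by 20 / 3 = 6.67 months has probability P(Poisson(20) ≥ 20) = 0.53. Deleting the words per site would leave on-plan recruitment close to a coin toss for Green.

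**The case against.** A reader might infer that a study recruiting to plan *is classed Red*. The text does not establish this. The Red accrual item is linked by *and* to attrition above 40%, and if the two are required jointly, low attrition keeps the study out of Red. The any-one rule, and the same *and* linking whole groups of criteria in that list, make the separate reading plausible without settling it. Red is also not automatic: it follows a review, and a negative recommendation is only a possibility. This objection stands, and it limits the claim to the accrual cut.

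A reader might also infer from the unqualified 3 per month in the Amber alternative that per site is a slip. That is possible, but per site appears in all three bands, and a single omission may be shorthand. The documents do not show which unit was intended.

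Staggered site opening would reduce the site-months and raise the per-site rate. It is unlikely to rescue the criterion: 20 recruits reach the Red cut only with 20 / 2 = 10 or fewer site-months, and Green only with 20 / 3 = 6.7 or fewer, against 14 planned.

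Finally, this is a descriptive single-arm feasibility study, accrual is one indicator among several, and the committee will see the actual rate and the reasons for it. So it would be too strong to say that good and bad recruitment cannot be told apart. The threshold is misplaced, but the information is not lost. No estimate and no participant's safety is affected.

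**Conclusion.** The inconsistency is real and follows from the protocol's own figures. On-plan accrual is 1.43 to 1.50 per site per month, about half the Green threshold of 3 and below the Red cut of 2. A study that delivers its recruitment plan exactly cannot be Green under any reading of the trigger logic. Whether it would also trigger Red cannot be decided from the text.

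The per-site rates assume two sites open for all seven months. The probabilities of about 0.3% and 88% further assume Poisson accrual at 3 per month. The failure to reach Green at the planned rate does not depend on the Poisson assumption.

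**What to change.** 1. Use one unit, overall or per site, in Section 9.3 and in all three bands of Section 14.7, including the Amber clause on the later recruitment months.
2. Anchor Green to the plan itself: 20 recruited within seven months, about 2.86 per month overall or 1.43 per site. Set Amber and Red below that on the same basis.
3. State whether accrual and attrition are separate or joint triggers in Amber and Red.
4. Say how site-months are counted if the sites open at different times.

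If the per-site rates were truly intended, Section 9.3 would have to change to 6 per month over about 3.3 months. That doubles the planned recruitment rate and is no longer a matter of wording.

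The cost of items 1 to 4 is a protocol wording amendment and a note to the Study Steering Committee and the funder, with no extra participants or data. The change should be made before accrual results are known.
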